Results comparable to those observed in obese adults have also been reported in obese children. Peak GH concentration after stimulation testing is lower in obese children compared to controls in studies using arginine and L-dopa, clonidine, and dexamethasone as stimuli. As with adults, obese children show a blunted degree of GH secretion during exercise, and do not respond to a glucose load. A study of 24-hour GH secretion in boys demonstrated an inverse correlation between BMI SDS and daily GH production rate, as well as mass and amplitude of each burst of GH. Similarly a study comparing lean and obese children showed the lean female subjects had greater GH secretion during periods of sleep and higher and more frequent GH peaks during the day compared to their obese counterparts; the trend was similar in lean versus obese males but without achieving statistical significance. Similar studies of sleep-associated GH release show fewer and smaller peaks of secretion in obese children compared to lean. Weight loss reverses these trends with 24-hour GH secretion among formerly obese prepubertal children whose BMI returned to the normal range mirroring that of a control population. Even short term calorie restriction showed a 60% improvement in average GH secretion.

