#### Main Study: Randomization

Only subjects meeting the inclusion and exclusion criteria during the screening visit will be randomized. Subjects will be assigned to receive placebo x 4 doses on the first day of GH stimulation testing and niacin 500 mg x 4 doses on the second day or they will be assigned to receive niacin 500 mg x 4 doses on the first day and placebo x 4 doses on the second day. Subjects

will be stratified by group and sex in blocks of 4 such that roughly equal numbers of subjects in each stratum will be assigned to each placebo and active medication administration order.

Additionally randomization of obese subjects will be stratified by BMI (95-99th percentile or >99th percentile).

Main Study: Inpatient evaluation:

Only subjects meeting the inclusion and exclusion criteria during the screening visit will be evaluated as inpatients. A total of 40 subjects in the two main groups will complete inpatient evaluation, although up to 50 may initiate inpatient evaluation in order to achieve full enrollment. The inpatient visit will occur within two months of screening visit to ensure consistency of physical exam and medical history throughout the study period. Patients will be admitted the night before the first day of testing. Additionally, literature suggests that several vitamins influence growth hormone secretion; thus, if applicable, vitamin supplements will be discontinued for three days prior to admission. All subjects will be admitted to the NIH Clinical Center for an evaluation that will include:

1. **Medical History and Physical Examination** with Tanner pubertal staging and anthropometric measurements including weight (in kg) and height (in cm) by stadiometer (3 repeated measures).
2. **DXA scanning** for determination of lean body mass and body fat mass.
3. **Placement of an intravenous line** to be used for medication administration and blood sampling over a 48 hour time period.
4. **Repeat urine pregnancy test** in girls age 10 and older.
5. **Overnight Fast** beginning at 10 pm on both nights; ending after completion of testing each day.
6. **Growth Hormone Stimulation testing** consisting of arginine (500 mg/kg IV up to maximum of 30 g, infused over 30 min) at 8:30am, followed by L-dopa (500 mg by mouth)

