### **Data Analysis**

Primary research outcome will be niacin-induced changes in arginine and L-dopa stimulated GH concentrations, measured as both area under the curve and peak values, in the overweight group compared with the control group. Secondary research outcomes will include changes in free fatty acid, glucose, and insulin concentrations during the GH stimulation tests. Since non-completion of the study is expected to be due to technical failures (e.g., nonfunctioning IVs) rather than subject factors, all analyses will be limited to subjects who complete both placebo and niacin studies. We do expect that some members of the control group will not reach a peak GH concentration of 7 ng/mL during the stimulation testing. We will report all control subjects in the final analyses. Analyses will be performed with age, Tanner stage, and initial BMI-SDS as covariates. Furthermore, tertiary analyses will also be performed to compare subjects in the Tanner I, Tanner II, and Tanner III groups to determine if any differences exist among these pubertal development stages. This analysis will be for exploratory purposes only; the study is not powered for this subgroup analysis. Additionally if any members of the control group have abnormally elevated lipid levels, we will specifically examine these subjects and their growth hormone concentrations. The primary outcome analysis will therefore be a repeated measures ANCOVA with subject group (obese and control) as the between factor, treatment (niacin or placebo) as the repeated measure, GH concentration (peak and AUC) as the outcome variables, and age, sex, and Tanner pubertal stage as covariates. We will also model the subject group by treatment interaction but no other interaction terms will be entered into the primary analysis.

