### **Randomization**

For randomizing order of administration of niacin and placebo, investigators will assign consecutive code numbers to participants from prespecified lists stratified by group, sex, and BMI (95-99th percentile or >99th percentile). The NIH Clinical Center Investigational Drug Management and Research Section will use permuted blocks with stratification to generate the allocations that translate code numbers into study group assignments by using a pseudo-random number program. Pharmacy personnel not otherwise involved with the conduct of the study will dispense study capsules in containers that appear identical and differ only by participant code number. No participant, investigator, or other medical or nursing staff interacting with participants will be aware of study group assignments during the trial.

Arginine hydrochloride 10% solution is approved by the FDA for growth hormone testing. This agent is available through the NIH pharmacy and is on the formulary. It will be used at a dose of 500 mg/kg IV up to maximum of 30g infused over 30 min on two consecutive days. This dosing corresponds to 5 mL/kg, with a maximum dose of 300 mL on two consecutive days.

L-dopa is not approved by the FDA for growth hormone testing, but is approved for other uses. L-dopa has been used clinically for many years for the purpose of growth hormone testing. L-dopa powder will be obtained from Spectrum Chemicals, which has supplied us with a Certificate of GMP. From 2011-2016, L-dopa was packaged, supplied, and distributed to the inpatient staff by the NIH pharmaceutical development section as 250 mg capsules. The analytical group of

Pharmaceutical Development Service conducted testing according to USP standards for medications used in this protocol prior to release for human consumption. Starting in mid-2017, Pine Pharmaceuticals will compound the 250 mg capsules and perform bioburden testing per the United States Pharmacopeia (USP) <61> and <62> standards. Purity and stability testing will be performed by the NIH Investigational Drug Management and Research Section, which will track and dispense all medications to the inpatient staff.

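### Treatment order in obese children is stratified by BMI, but no analysis uses that stratum: nest it within the obese group and prespecify an exploratory severity analysis

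*Combined protocol and SAP*

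**What the plan says.** Main Study: Randomization stratifies by group and sex, and then adds "Additionally randomization of obese subjects will be stratified by BMI", with cut-points 95-99th and above the 99th percentile. The Randomization section under Pharmaceutical information repeats this, assigning code numbers "from prespecified lists stratified by group, sex, and BMI". That section opens "For randomizing order of administration of niacin and placebo", so what is allocated is the order of the two treatments. Every child is to receive both.

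Data Analysis gives two covariate statements. The general one is: "Analyses will be performed with age, Tanner stage, and initial BMI-SDS as covariates". The primary repeated measures ANCOVA then has group as the between factor and treatment as the repeated factor, "and age, sex, and Tanner pubertal stage as covariates". Group by treatment is modelled, but "no other interaction terms will be entered into the primary analysis". A comparison across Tanner stages is planned as exploratory and stated to be unpowered. No analysis names the BMI stratum.

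Under Inclusion Criteria, obese children have BMI at or above the 95th percentile and controls lie between the 5th and 85th. Specific Hypotheses includes two comparisons between different children: peak GH in controls against obese children, and obese children on niacin against controls on placebo.

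**The concern.** Of the three factors used for allocation, group and sex reach the primary model and the BMI stratum does not. The protocol itself gives reason to think the stratum predicts GH level. Its background section on GH in obesity cites, in boys, "an inverse correlation between BMI SDS and daily GH production rate", and the Introduction cites a negative association between BMI SDS and stimulated peak GH.

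Three things are at stake:

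- The between-child hypotheses lose some precision if a known predictor of GH level is left out.
- If BMI-SDS is used instead, as the general sentence says, it competes with the group term for the obese-control difference those hypotheses concern.
- Pubertal stage has a declared exploratory comparison and obesity severity has none, although the Objectives include explaining reduced GH secretion in obesity. A comparison within obese children is also free of short stature and referral for GH testing, which separate the two groups as well as BMI.

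**Working it through.** The plan gives no figure for this point, so there is none to reproduce. The checks below borrow the planning inputs from Determination of Sample Size.

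**1. Which factors are used where**

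| Factor | Allocation | General covariate sentence | Primary model |
|---|---|---|---|
| Group | yes | not listed | yes |
| Sex | yes | no | yes |
| BMI stratum (obese only) | yes | no | no |
| BMI-SDS | no | yes | no |
| Age, Tanner stage | no | yes | yes |

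**2. Can BMI-SDS stand in for the stratum?** The 95th, 85th and 5th percentiles are standard normal values of 1.64, 1.04 and -1.64. Obese children therefore have BMI-SDS of at least 1.64, and controls lie between -1.64 and 1.04. The ranges do not overlap. With BMI-SDS entered across both groups, the group term becomes a difference at a common BMI-SDS where at most one group has children. A stratum indicator that varies only among obese children does not have this problem.

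**3. Primary contrast (niacin minus placebo change, obese against control).** A stratum effect on GH level is present on both days and drops out of each child's change. A stratum difference *d* in niacin response does not drop out.

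Inputs: SD 6.1 (Determination of Sample Size, taken as the SD of change) and 20 completers per group. Assumed: equal strata, and the values of *d*.

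- Obese-group SD = sqrt(6.1² + d²/4)
- SE of contrast = sqrt(SD_obese²/20 + 6.1²/20)

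| d (micrograms/L) | Obese SD | SE | Increase |
|---|---|---|---|
| 0 | 6.10 | 1.93 | none |
| 2 | 6.18 | 1.94 | 1% |
| 5 | 6.59 | 2.01 | 4% |
| 8 | 7.29 | 2.13 | 10% |

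The last row is extreme: 8 is 78% of the whole 10.3 planning effect.

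**4. Sensitivity to the SD.** The 6.1 comes from a whole obese cohort, so it may already contain between-stratum variation. In that case the within-stratum SD at d = 5 is sqrt(37.21 - 6.25) = 5.56. The SE with the response difference modelled would be sqrt((30.96 + 37.21)/20) = 1.85 against 1.93 without, again about 4%. The planned sample sizes of 14 and 22 per group do not follow from an SD of 6.1 and would need about 9.0 to 9.4. This is a separate matter, but at SD 9.2 the increase is 0.3% for d = 2 and 1.8% for d = 5.

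**5. Between-child comparisons.** Assumed: between-child SD 5, within-child SD per day 6.1/sqrt(2) = 4.31, equal strata, stratum difference in level 5 micrograms/L.

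- Simulation of 20,000 crossover trials: the SD of change is 6.05 without the level effect and 6.06 with it, so it cancels. The between-child SD of the two-day mean rises from 5.81 to 6.10, about 5%.
- For a single day, as in the hypotheses: sqrt(25 + 18.6) = 6.60 becomes sqrt(43.6 + 6.25/2) = 6.84, about 3.5%. The 6.25 is 5²/4, halved because only one of the two groups carries it.

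**6. What a stratum comparison could show.** This uses 20 obese completers, SD 6.1, two-sided alpha 0.05 (sidedness is not stated in the plan) and the noncentral t with 18 df.

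| Split (assumed) | Detectable at 80% power | Power for 5 micrograms/L |
|---|---|---|
| 10/10 | 8.1 | 41% |
| 14/6 | 8.8 | 36% |
| 16/4 | 10.1 | 28% |

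At SD 9.2 the detectable difference is 12.2 to 15.2.

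**The case against.** The strongest reply is that little is lost. The primary outcome is a within-child change, from which a level effect cancels. The gradients the protocol cites concern GH level and do not show that niacin response varies with BMI. Weighting the two obese strata by their observed shares returns the ordinary obese mean apart from covariate adjustment, so the estimate will barely move. A continuous BMI-SDS analysis within obese children would use more information than two categories, and a 40-child pilot is right to limit its interactions. All of this stands, and it is why the primary interaction structure should stay as written.

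A reader might infer four stronger points, which the documents do not support:

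- *That stratum variation sits in the error of the primary test.* A level effect does not. Only a difference in niacin response does, and nothing in the documents shows one.
- *That the plan forbids a BMI-by-treatment analysis.* The restriction covers the primary analysis only. Elsewhere such an analysis is unplanned, not barred.
- *That a randomised severity comparison is being discarded.* Order is randomised and BMI category is observed, so the comparison is observational. BMI is measured on every child, so it also remains available.
- *That obesity degree is ignored throughout.* The general covariate sentence does list BMI-SDS. The difficulty is that the primary model omits it and that it is nearly collinear with group.

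The reply does not cover the between-child hypotheses, where the level effect remains, or the conflict between the two covariate lists.

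**Conclusion.** The point holds in a limited form and is a minor improvement. The BMI stratum is used for allocation and in no analysis, and the one BMI covariate the plan mentions is poorly suited to a two-group model with these entry criteria. For the primary contrast the SE is about 1% to 4% larger if niacin response differs between strata by 2 to 5 micrograms/L. For the between-child comparisons the SD is about 3.5% to 5% larger if GH level differs by 5 micrograms/L. The stratum differences, the equal split and the between-child SD of 5 are assumptions. The split in particular is unknown, and all seven children in Dose-Establishing Study 1 were above the 97th percentile. Any severity comparison is exploratory: only differences of about 8 to 10 micrograms/L would be reliably detected.

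**What to change.** In Data Analysis:

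1. Give one covariate list for the primary model: age, sex, Tanner stage, and the BMI stratum nested within the obese group (control, obese 95-99th, obese above the 99th percentile). Remove BMI-SDS as a covariate across both groups.
2. Define the obese-control contrast as the two obese levels weighted by their observed shares, minus control. If *p* is the share above the 99th percentile, coding the stratum term 1 - p and -p in obese children and 0 in controls makes the group coefficient equal to this contrast.
3. Keep group by treatment as the only primary interaction. The 1% to 4% in the primary SE is then accepted, and the nested term serves the between-child comparisons.
4. Prespecify, before unblinding, an exploratory and unpowered analysis, labelled like the Tanner comparison: niacin change and placebo-day GH by BMI stratum, or by continuous BMI-SDS within obese children. Describe it as an observational severity comparison.

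The cost is wording and one degree of freedom for the nested term, with no new data. Stratum estimates will be imprecise. With 10 children and SD 6.1, the SE of a mean change is 6.1/sqrt(10) = 1.93, and the 95% half-width is 2.262 × 1.93 = 4.4 micrograms/L.

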**Data Table 3: Reported Adverse Events During Niacin Dose-Finding Study 2**

Expected adverse reactions (%)	500 mg Niacin every hour (n=5)				
	Time (hours)				
	0	1	2	3	4
Headache	0	20	0	0	0
Flushing	0	100	40	40	0
Feeling warm	40	100	40	20	20
Nausea	20	20	40	0	20
Vomiting	0	20	0	0	20
Stomach Ache	20	40	20	20	20
Diarrhea	0	0	0	0	0
Tingling	0	60	20	0	0
Light-headedness	0	0	0	0	0
Itchiness	0	60	40	20	0
Rashes	0	0	0	0	0

Note: niacin doses administered at time 0, 1, 2, and 3. Time 0 data reflect reactions before the first dose was administered. The symptoms at hour 4 were of short duration with only moderate severity. The symptoms reported at earlier hours were also of mild or moderate intensity and, with the exception of feeling warm or flushing, of short duration. All symptoms had resolved completely by the end of the 4th hour.

We therefore will initiate the main study protocol.

During the main study, two sets of GH stimulation tests will be performed on two consecutive days. On one day, the testing will be performed in conjunction with four hourly doses of niacin 500 mg, and on the other day with four doses of a placebo, with the order (niacin first day or second) randomly determined. Subjects will not receive sex hormone “priming” pretreatment (which is used by some clinicians to overcome the naturally lower occurring GH concentrations found in prepubertal children) due to the design of the study; no protocols have established methodology for priming when performing GH stimulation testing on sequential days. We were concerned that administration of sex-steroids could differentially affect the first stimulation test compared to the second. Additionally it might be difficult to assure compliance with the medication as it would be taken at home prior to the admission. Furthermore this protocol will be restricted to

prepubertal and early pubertal subjects to limit the degree of sex hormone influence. It should also be noted that the vast majority of pediatric growth hormone testing performed in the US is done in the absence of such sex steroid priming.

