at 9:30am. A dose of niacin (dose determine in the dose-establishing study) or placebo will be administered by mouth at 7:30am, 8:30am, 9:30am, and 10:30am . The study will be repeated the next day in the same fashion. The order of niacin 500 mg or placebo will be randomized. Blood will be sampled from an indwelling intravenous line at times -60, -30, 0, +30, +45, +60 minutes of arginine infusion for measurements of GH, free fatty acids, glucose (via bedside glucometer), and insulin concentrations. Blood will also be sampled at times -30, 0, +30, +45, +60, +75, +90, and +120 minutes of L-dopa administration for the same serum concentrations. GHRH and Somatostatin will be sampled hourly at 7:30am, 8:30am, 9:30am, 10:30am, and 11:30am, with two additional measurements at +30 minutes (9am) of arginine infusion and +30 minutes (10am) of L-dopa administration. After completion of this sampling, the subject will be given an ad lib diet.

7. **Discharge:** Subjects will be discharged following the growth hormone stimulation test on the second day.

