**Adverse event reporting:**

Adverse events, protocol deviations, unanticipated problems (UP), Unanticipated Adverse Device Effects (UADEs), serious adverse events, sponsor and serious, are defined as described in NIH HRPP SOP 16 (“Reporting Requirements for Unanticipated Problems, Adverse Events and Protocol Deviations.”). All adverse events occurring during the study, including those observed by or reported to the research team, will be recorded. Serious unanticipated problems, and serious protocol deviations, will be reported to the IRB and CD as soon as possible but not more than 7 days after the PI first learns of the event. Not serious unanticipated problems will be reported to the IRB and CD as soon as possible but not more than 14 days after the PI first learns of the event. Not serious protocol deviations will be reported to the IRB as soon as possible but not more than 14 days after the PI first learns of the event.

Deaths will be reported to the Clinical Director within 7 days after the PI first learns of the event.

The PI will immediately report SAEs to the Sponsor according to the requirements of 21 CFR 312.64(b) and as agreed upon with the sponsor. The PI will record nonserious AEs and report them to the Sponsor according to the timetable for reporting specified in the protocol (21 CFR 312.64(b)).

A post test questionnaire will be administered after the inpatient admission in the main study, and the questionnaire will also be administered every hour from 6am to Noon during the inpatient

admission in the dose-establishing study. A sample questionnaire is attached to the end of this document as Appendix D.

**Waiver of Reporting to the IRB of anticipated minor protocol deviations, adverse events and deaths due to underlying disease or population under study unless determined to be an Unanticipated Problem**

- For waiver of Reporting to the IRB of anticipated minor protocol deviations

The following anticipated minor deviations in the conduct of the protocol will not be reported to the IRB unless they occur at a rate greater than that which is anticipated to occur:

Problem	Expected Frequency
Rescheduled appointment for protocol visit	50%
Inability to obtain intravenous access after 2 attempts	25%
Venous sample at a time point not obtained	25%
Hemolysis or other issue preventing analysis of a blood or urine sample	25%
A research subject was enrolled but did not meet eligibility criteria	5%

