##### Day 2:

7:30am and 8:30am: placebo or niacin 500 mg  
7:30am, 8am, and 8:30am: Blood draw (Note GHRH and Somatostatin measured 7:30am and 8:30am)  
8:30am: Arginine stimulation test per routine protocol - 500mg/kg up to 30g  
8:30am, 9am, 9:15am, 9:30am , : Blood draw (Note: GHRH and Somatosatin measured 9am)

9:30am: Placebo or niacin 500 mg and start L-dopa stimulation test – 500 mg  
 9:30am, 10am, 10:15am, 10:30am, 10:45am, 11am, 11:30am:  
 Blood draw (Note: GHRH and Somatostatin measured 9:30am 10am 10:30am, and 11:30am)  
 10:30am: Placebo or niacin 500 mg  
 11:30am: completion of test, resume ad lib diet then discharge

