## Appendix D

### Post-Test Questionnaire

To be administered hourly from 6am-Noon during the inpatient stay of the dose-establishing study and at the end of the inpatient stay of the main study

Please check off the symptoms that the patient experienced during the time the patient as staying at the NIH. Then indicate how long it lasted and how severe it was.

Symptom	Present?	Duration	Severity (please choose one)		
			1 (mild)	2 (moderate)	3 (severe)
Headache					
Flushing of face					
Feeling warm					
Nausea (feeling like vomiting)					
Vomiting					
Stomach ache					
Diarrhea or loose stools					
Tingling in arms or legs					
Light-headed or faint					
Itchiness					
Rash or skin problems					
Other (please list):					

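### Scheduled adverse-event follow-up after the last niacin dose is about 1 hour or about 25 hours depending on treatment order, and the single questionnaire cannot assign late or continuing symptoms to a test day

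*Combined protocol and SAP*

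**What the plan says.** Main Study: Inpatient evaluation, item 6, has niacin "or placebo will be administered by mouth at 7:30am, 8:30am, 9:30am, and 10:30am" and repeats the test the next day with the other treatment. Item 7 states that "Subjects will be discharged following the growth hormone stimulation test on the second day". Appendix C, Main Study, Day 2, adds a clock time: "11:30am: completion of test, resume ad lib diet then discharge".

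The section on adverse event reporting gives the main study one symptom instrument: "A post test questionnaire will be administered after the inpatient admission in the main study". Appendix D places it "at the end of the inpatient stay of the main study", whereas the dose-establishing studies used it hourly. Its instruction reads "Please check off the symptoms that the patient experienced during the time the patient as staying at the NIH". The columns are presence, duration and severity; there is none for test day or onset time.

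The monitoring section describes two visits, and Appendix B lists only the baseline evaluation and the inpatient admissions. The reporting section also says "All adverse events occurring during the study, including those observed by or reported to the research team, will be recorded", without stating when that period ends. The data safety monitoring board (DSMB) receives the questionnaire data and side-effect reports as a comparison of A with B, supplemented by the investigators' manual review.

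**The concern.** The two orders give different lengths of scheduled observation after niacin. A child given niacin second leaves soon after the fourth capsule. A child given niacin first stays another day, but the end of that period overlaps the placebo test. Because the form asks once about the whole stay, the data it yields do not show on which day a symptom began.

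Three uses of the safety data are affected. The first specific hypothesis includes an absence of significant adverse effects. The DSMB is asked whether niacin is safe. The waiver of reporting to the IRB sets its expected frequencies hour by hour, which a form without onset times cannot be checked against.

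**Working it through.** The plan states no adverse-event rate or precision for this comparison, so there is no figure to reproduce.

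**Windows** (dose times from item 6, end of test from Appendix C)

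- Niacin second, last dose to end of day 2 test: 10:30am to 11:30am on day 2 = 1 h. This is a minimum, since a meal comes before discharge and no discharge time is fixed.
- Niacin first, last dose to end of day 2 test: 10:30am on day 1 to 11:30am on day 2 = 25 h. Of these, 21 h come before the first placebo capsule at 7:30am and 4 h overlap the placebo test.
- From the first niacin dose: 4 h and 28 h.

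**Children affected.** Order is allocated about equally, in blocks of 4, with 40 completers planned: 40 / 2 = about 20 with the short window.

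**Could reactions fall outside 1 h?** Dose-Establishing Study 2 used the same hourly 500 mg × 4 schedule, so its hour 4 is 1 h after the last dose (n = 5; 20% is one child). The last column is from the table of expected reactions by time point in the waiver section.

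| Symptom | Study 2, pre-dose | Study 2, hour 4 | Expected, hour 4 |
|---|---|---|---|
| Feeling warm | 40% | 20% | 60% |
| Nausea | 20% | 20% | 0% |
| Vomiting | 0% | 20% | 0% |
| Stomach ache | 20% | 20% | 0% |

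Taken at face value, the expected-reaction table bounds the share of children whose first report could come after hour 4. For each symptom the bound is min(100% − highest rate at hours 1–4, highest rate at hours 5–6):

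- Flushing: min(100 − 100, 50) = 0.
- Feeling warm: min(100 − 100, 20) = 0.
- The other nine symptoms are 0% at hours 5–6, so the bound is 0.

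On that table only the duration of flushing and warmth would be cut short. But Study 2 disagrees with it at hour 4 for nausea, vomiting and stomach ache, so the bound is not secure.

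In Study 1, after 500 mg at hour 0, nausea and vomiting were each 0% at hour 1 and 20% (1 of 5) at hour 2. If the hour 2 report preceded the second dose, which the table does not say, those symptoms appeared more than 1 h after a dose.

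**Size under an assumption.** The documents give no rate for late-onset events. For an assumed rate p, the expected number among 20 niacin-second children is 20p, and the chance of at least one is 1 − (1 − p)^20.

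| p | Expected of 20 | P(at least one) | Crude rate over 40 if none of these is captured (p/2) |
|---|---|---|---|
| 1% | 0.2 | 0.18 | 0.5% |
| 5% | 1 | 0.64 | 2.5% |
| 10% | 2 | 0.88 | 5% |

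The dose-establishing studies cannot rule such rates out. Even had all children been followed for longer with no late event, the one-sided 95% upper limits would be 1 − 0.05^(1/5) = 45% for 5 children and 1 − 0.05^(1/7) = 35% for 7.

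**The case against.** A reader might infer that niacin reactions are under-counted in half the sample. The documents do not support that, for these reasons.

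- **Reactions are mostly early.** In both dose-establishing studies flushing, warmth and itching are already frequent at the first hourly reading. In Study 1 every listed symptom was 0% at hour 6, 2 h after the last dose. This stands for the common reactions. It is weaker for the main study, because Study 1 gave three doses (1,500 mg) two hours apart rather than four hourly ones (2,000 mg), and neither study added arginine or L-dopa.
- **The hour 4 rates are not a clear signal.** Three of the four equal or fall below their pre-dose values; only vomiting exceeds its pre-dose value, by one child. This stands.
- **Study 2 does not contradict itself on resolution.** The protocol says "The symptoms at hour 4 were of short duration with only moderate severity" and that all symptoms had cleared by the end of the fourth hour. Appendix C puts completion at noon, half an hour after the hour 4 reading, so later observation may lie behind that statement. This stands.
- **Recording does not stop at discharge.** Reported events are still recorded, and the investigators' review can add others. Only scheduled questioning ends. This stands.
- **The direction is open.** Niacin-first children recall niacin-day symptoms about a day later, which could lower their counts. Their longer window includes a second arginine and L-dopa test, and the protocol lists nausea and vomiting for both agents. Across two equal orders, niacin and placebo each average (28 + 4) / 2 = 16 h from first dose to end of stay. Nor does any rule assign a late niacin symptom to placebo; the form simply cannot tell.

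What remains is that a late niacin event has scheduled ascertainment in only one order, and there it cannot be separated from the placebo day.

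**Conclusion.** The point holds as a gap in the safety data collection. Scheduled ascertainment after the last niacin dose is at least about 1 h in one order and about 25 h in the other. No contact follows discharge, the end of the adverse-event period is undefined, and the only scheduled form cannot separate test days. Late or continuing reactions are therefore captured unequally by order and cannot be cleanly assigned in the A-versus-B review.

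An actual under-count of niacin reactions is not shown, and neither the size nor the net direction of any bias can be derived from the documents. The figures for late-onset events rest on assumed rates of 1% to 10%. The windows assume discharge soon after 11:30am and about equal numbers in each order.

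Adverse events are not a listed primary or secondary outcome, and the growth hormone endpoints are unaffected. Severity: minor.

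**What to change.** - Complete Appendix D once for each test day, adding fields for test day and onset time.
- Specify that niacin and placebo are compared over the same fixed window from each day's first dose. The 4 h from 7:30am to 11:30am are available for both treatments in both orders. Report later events separately by order.
- Add one scripted call to each family about 24 h after discharge. Appendix D asks only about the stay, so its recall period must be reworded to cover the time since discharge.
- State when the adverse-event period ends, and enter the call in the adverse event reporting section and in Appendix B.

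The cost is slightly more form-filling and one short call per family by existing staff. Late symptoms reported by parents will be less precise than ward observation.
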